Postpartum Non-pharmacologic Pain Management – Randomized Controlled Trial

Investigators: [name] (PI), [name], [name], DO, [name]

NCT03903172

Postpartum Non-pharmacologic Pain Management – Study Protocol

Investigators: [name] (PI), [name], [name], DO, [name]

Objective

To examine whether use of an abdominal binder for postpartum patients after vaginal delivery can effectively manage their pain and reduce the need for pharmacologic analgesics

Aims

1. To determine whether use of an abdominal binder on postpartum days zero and one will result in decreased patient pain as measured by pain scores on a visual analog scale of one to ten
2. To determine whether use of an abdominal binder for postpartum patients will reduce the quantity of non-narcotic pain medications given on postpartum day zero and one
3. To determine whether use of an abdominal binder for postpartum patients will reduce the quantity of narcotic pain medications given on postpartum day zero and one

Hypothesis

Use of an abdominal binder postpartum after a vaginal delivery will be associated with lower pain scores and reduced need for pharmacologic analgesics.

Background

A significant part of postpartum care involves management of patients' pain and discomfort. Etiologies of this pain include perineal pain, incisional pain, uterine involution pain, and pelvic girdle and lower back pain. Postpartum pain management primarily focuses on the former three types of pain: perineal, incisional and uterine involution. In a review of the management of postpartum pain, Eshkevari et al¹ discuss several well-established pain management strategies employed for postpartum patients, including ibuprofen and other NSAIDs for uterine involution pain and inflammation; local anesthetics for perineal lacerations or episiotomies; warm or cold compresses for perineal pain; and opioids for post-operative or poorly controlled postpartum pain.

Data regarding management of pelvic girdle and lower back pain is scarce and the limited literature available primarily focus on the pregnant patient. Different proposed treatment or management strategies

during pregnancy include physical therapy, targeted exercises, acupuncture, NSAIDS and opioids³. Approximately 25% of postpartum women endorse pelvic girdle and/or lower back pain², and these types of pain can persist for as long as several weeks to 1-2 years after delivery³. Therefore, management remains key for the postpartum patient as well. The proposed pathophysiology behind pelvic girdle pain and lower back pain in the context of pregnancy is widening of the pubic symphysis and increased laxity in the sacro-iliac joints (SIJ) secondary to both biomechanical shear forces of increased weight bearing and elevated levels of relaxin, a polypeptide hormone that increase laxity of ligaments³. A prospective study investigating the impact of abdomino-pelvic belts at different positions on the laxity of the SIJ found that use of the abdomino-pelvic belt significantly decreased mobility of the SIJ⁴. Additionally, pelvic belts or abdominal binders may help provide stability to muscles of the abdomen, back and spine^{4,5}.

Studies investigating the use of abdominal binders for pain management in post-operative patients following both cesarean section and gynecologic surgery have had mixed results. A randomized control trial examining impact of abdominal binders on patient reported pain and symptom distress found no significant difference in pain on post-operative days one and two, and the difference in distress on post-operative day two was no longer statistically significant after correction for multiple measures⁶. Another study involving gynecologic surgery patients randomized to abdominal binder or control groups found that there was no overall significant difference in morphine use or pain scale between the groups, and the benefits were limited to a significant effect on post-operative ambulation for a subset of patients with highest risk of complications: patients > 50 years, cancer patients, and those with vertical incision. In contrast, a more recent randomized controlled trial assessing abdominal binders following cesarean delivery found that pain and symptom distress scores were significantly lower at all time points in comparison to a control group⁷.

A common theme in the current literature regarding postpartum pain management is the need for more research^{1,3,7}. In light of the current opioid abuse epidemic, which affects approximately 2.1 million people and the U.S Department of Health and Human Services declared a public health emergency in 2017⁸, there is a renewed emphasis utilizing non-opioid methods on pain control. As a primary source of pain in the postpartum period is associated with musculoskeletal pelvic discomfort, the use of a supportive abdomino-pelvic belt may be a non-pharmacologic modality that could reduce pain and decrease narcotic requirements in postpartum patients. No studies to our knowledge have directly assessed the effectiveness of abdominal binders on pain management in postpartum patients. This study aims to examine how use of an abdominal binder might impact postpartum pain, and the use of pharmacologic analgesia following vaginal delivery.

Protocol

- Recruitment
 - o We will evaluate patients admitted to Labor and Delivery for potential participants in our study based on the inclusion and exclusion criteria outlined below. If appropriate to approach, eligible potential participants will be approached in their labor and delivery room prior to delivery. If interested in participation, the Informed Consent document will be presented and explained in the room to ensure privacy.
- Inclusion Criteria
 - o 18 years of age and older
 - o Pregnant
 - o Admitted to labor and delivery
 - o Anticipated spontaneous vaginal delivery
 - o Informed consent obtained
- Exclusion Criteria
 - o Documented chronic pain condition
 - o Chronic narcotic use or Maternal Abstinence Treatment
 - o UDS positive for opiates on admission
 - o Trial of labor after cesarean
 - o Lack of sufficient English proficiency to obtain informed consent
 - o Cesarean section or operative vaginal delivery
- Subject Informed Consent
 - o Informed consent process will take place at the Berry Women's Center at Miami Valley Hospital
 - o Written and signed consent will be obtained in English.
- Plans of obtaining informed consent:
 - o Potential eligible participants will be approached in the labor and delivery room to ensure privacy. The research assistant will provide and discuss an informed consent form with

the participant. The informed consent form will describe the project goals, length and rational, as well as the types of PHI that will be collected. All participants who agree to participate in the study will sign the informed consent form. All participants will be provided with a copy of the signed consent form.

- Study design & procedures
 - o After signing informed consent, participants will be assigned to the intervention or control group via block randomization
 - o Those participants in the standard of care group will receive routine postpartum care
 - o Those participants in the intervention group will receive an abdominal binder in addition to routine postpartum care
 - Determination of appropriate binder size will be based on a visual assessment of the patient's abdominal circumference
 - o Nursing staff will evaluate participant's pain level using a visual analog scale of 1-10 a minimum of every 4 hours. Patient reported pain score and pain location will be recorded in the participant's electronic medical record. These processes do not deviate from current standards of care and documentation.
 - o Additional non-pharmacologic pain relief measures utilized by patients will be documented on the data collection sheet attached to the patient's chart. These measures include heating pad, ice pack, and tucks pads
 - o All medications received will be documented in the electronic medical record per usual documentation protocols
 - o Nursing staff will document compliance of patient for wearing the abdominal binder, making notes when the binder was removed and if/when it was put back on.
- Sample Size Estimation & Data Analysis Plan
 - o Sample size was estimated using G*Power. In order to detect a difference between groups on pain scores and use of pain medications, we will need to enroll 65 patients per group. This will enable us to detect a moderate difference (i.e., medium effect size) between the groups with a power = 80% and p at <0.05. We will enroll an additional 10 patients to account for dropouts for a total N=140.
 - o The two groups will be compared for 1. reported pain scores (assessed by nursing staff and documented in the EMR) and for 2. pain medications used (morphine equivalent as

recorded in the MAR) for the duration of patients' hospital stay. Repeated measures analysis of variance will be used to determine differences between the groups over time.

- Data collection plan
 - o Prospective data collection with hard copy data entry form that includes PHI for participant identification, basic demographic information, delivery information (see separate document), non-pharmacologic pain relief measures used
 - o Electronic medical record review for: pain scores, pain location, medications received
 - Pain score immediately postpartum
 - Pain scores on PPD#0 and PPD#1
 - Patient reported pain locations
 - Quantity of non-narcotic pain medication received on PPD#0 and PPD#1
 - Quantity of narcotic pain medication received on PPD#0 and PPD#1
 - Compliance wearing the abdominal binder
- Risks
 - o Allergic reaction to fabric of abdominal binder
 - o Skin irritation
 - o Increased discomfort or pain with use of abdominal binder
- Mitigation of risks
 - o If participants experience an allergic reaction or skin irritation from the abdominal binder they will be offered symptomatic treatment. Participants in the experimental arm will be encouraged to keep the abdominal binders in place for 24 hours postpartum, but will be permitted to remove the abdominal binder at any time should they find it causing irritation, increased pain or any other adverse reaction.

References

1. Eshkevari, L, et al. "Management of Postpartum Pain." *Journal of Midwifery and Women's Health*, vol. 58, no. 6, 2013, pp. 622–631.
2. Wu WH, et al. "Pregnancy related pelvic girdle pain (PGP), I: terminology, clinical presentation, and prevalence." *European Spine Journal*, vol. 13, 2004, pp. 575–589.

3. Vermani, E, et al. "Pelvic girdle pain and low back pain in pregnancy: a review." *Pain Practice*, vol. 10, no. 1, 2009, pp. 60-71.
4. Mens JMA, et al. "The mechanical effect of a pelvic belt in patients with pregnancy-related pelvic pain." *Clinical Biomechanics*, vol. 21, 2006, pp. 122-127.
6. Gillier, CM, et al. "A randomized controlled trial of abdominal binders for the management of postoperative pain and distress after cesarean delivery." *International Journal of Gynecology and Obstetrics*, vol. 133, 2016, pp. 188-191.
7. Ghana, S, et al. "Randomized controlled trial of abdominal binders for postoperative pain, distress, and blood loss after cesarean delivery." *International Journal of Gynecology and Obstetrics*, vol. 137, 2017, pp 271-276.

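### Assignment follows a pre-delivery consent and nothing makes it wait for delivery, although delivery mode is an exclusion; opening the allocation after a confirmed spontaneous vaginal delivery is a cheap improvement

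*Protocol*

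**What the plan says.** - **Approach and consent (Protocol, Recruitment).** "eligible potential participants will be approached in their labor and delivery room prior to delivery".
- **Inclusion Criteria.** The delivery-mode criterion is an expectation: "Anticipated spontaneous vaginal delivery".
- **Exclusion Criteria.** The matching exclusion concerns the actual mode: "Cesarean section or operative vaginal delivery".
- **Assignment (Study design & procedures).** "After signing informed consent, participants will be assigned to the intervention or control group via block randomization". The section adds no later trigger and no check of delivery mode before assignment.
- **Numbers (Sample Size Estimation & Data Analysis Plan).** "we will need to enroll 65 patients per group", and then "We will enroll an additional 10 patients to account for dropouts for a total N=140". Dropout is not defined, and nothing says whether a woman excluded for delivery mode is replaced or counted.
- **Baseline pain (Data collection plan).** The list of scores begins with "Pain score immediately postpartum". This appears to be the baseline pain score that the SAP compares between groups.
- **Analysis.** The SAP uses Student's t-test for average pain on each of the two postpartum days and names no analysis population. The protocol names repeated measures ANOVA.

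The Data collection plan also refers to a separate document for delivery information, which was not available for this review.

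**The concern.** The binder is used only after delivery, and eligibility depends on how delivery goes. If the allocation is opened at consent in labor, every woman who then has a cesarean or operative vaginal delivery has been randomised and is ineligible before she could have used a binder.

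Three things follow on that reading. Blocks lose members after assignment. If these women count toward the 140 and are not replaced, they share an allowance of 10 with ordinary dropout. The analyst also has to decide later how to treat them, because neither document says. None of this buys anything, since nothing in the documents requires the arm to be known before delivery.

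**Working it through.** **1. Inputs.** From the protocol: 65 per group, 10 extra, 140 in total, 80% power, 0.05 significance, and a target described only as a medium effect. Assumed: d = 0.5 (f = 0.25 for ANOVA), a two-sided test, 1:1 allocation. The documents give no delivery-mode rate, so every loss rate below is an assumption.

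**2. Reproducing the plan's figure.** Two-sample t-test with noncentral t, δ = d × √(n₁n₂/(n₁+n₂)).

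- 64 per group: δ = 0.5 × √32 = 2.828, power 80.1%. This is the smallest n that reaches 80%.
- 65 per group: δ = 0.5 × √32.5 = 2.850, power 80.8%.

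The stated 65 therefore fits a two-sided t-test at d = 0.5. The dropout allowance is 10/140 = 7.1%.

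**3. Illustration under the SAP's t-test.** 140 are randomised, losses from all causes are not replaced, and arms are as equal as possible.

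| Assumed total loss | Analysable | Power |
|---|---|---|
| 5% | 133 | 81.6% |
| 7.1% (the allowance) | 130 | 80.8% |
| 10% | 126 | 79.5% |
| 15% | 119 | 77.2% |
| 20% | 112 | 74.6% |
| 25% | 105 | 71.8% |
| 30% | 98 | 68.8% |

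The effect detectable with 80% power moves from d = 0.495 at 130 to 0.503 at 126 and 0.534 at 112.

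**4. The same question under the protocol's repeated measures ANOVA.** Between-group test, f = 0.25, λ = f² × N × m / (1 + (m − 1)ρ), degrees of freedom 1 and N − 2. The table gives the smallest even N for 80% power; tolerated loss is 140 − N. The number of measures m and the correlation ρ are assumptions.

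| m | ρ | N needed | Tolerated loss of 140 |
|---|---|---|---|
| 2 | 0.5 | 98 | 42 (30.0%) |
| 2 | 0.7 | 110 | 30 (21.4%) |
| 2 | 0.8 | 116 | 24 (17.1%) |
| 6 | 0.5 | 76 | 64 (45.7%) |
| 6 | 0.7 | 98 | 42 (30.0%) |
| 6 | 0.8 | 108 | 32 (22.9%) |

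The precision question therefore belongs mainly to the SAP's t-test.

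**5. After the change.** With 140 randomised after delivery, delivery mode removes nobody from the randomised set. If all 10 allowed dropouts occur, 140 − 10 = 130 remain and power is 80.8%. The loss moves to before randomisation. Consents needed are 140/(1 − q), rounded up: 148 (q = 5%), 156 (10%), 175 (20%) and 200 (30%).

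**The case against.** **Timing is a reading, not a fact.** Assignment after consent fixes an order and no clock time. Assignment after delivery would also comply, and the steps that follow it (routine postpartum care, the binder, sizing) fit that equally well. A team that applied the full exclusion list before assigning would have to wait for delivery. This stands. A reader might infer that the protocol demonstrably randomises in labor; it does not say so. It only fails to prevent it. The separate delivery-information document might also contain a check.

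**No shortfall is shown.** A reader might infer that the trial is underpowered. That needs assignment in labor, excluded women counted in the 140, no replacement, and a loss rate that the documents do not give. If these women are replaced or not counted, there is no shortfall. The shifts in detectable effect are also small at moderate loss, and the protocol's own ANOVA largely absorbs them. All of this stands and limits the point to an illustration.

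**Bias.** A reader might infer that post-randomisation exclusions bias the comparison. Delivery mode is settled before the binder is used, so losses should be similar by arm. Bias would need exclusions that depend on the arm, and nothing in the documents indicates that.

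**The remedy has its own risk.** Opening an allocation after staff know the delivery course and the pain score gives room for selective entry, in a trial where the binder is visible and the protocol describes no concealment method. This is a fair objection, so concealment and randomisation of every eligible consented woman must be part of the change.

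**Conclusion.** The point holds as a cheap improvement in design. The documents support four statements: consent precedes delivery, assignment is the next stated step, actual delivery mode is an exclusion, and no step makes assignment wait for it. On the natural reading, some randomised women become ineligible before the intervention begins.

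The expected cost is precision, and its size is unknown. The only figures available are conditional ones, resting on the assumed effect size, two-sidedness, loss rate and absence of replacement; they apply chiefly to the t-test. It would also go too far to say that the plan overlooks these women. It does exclude them; what it leaves open is whether they are replaced, whether they count in the 65 per group and the 140, and how they are analysed. Confidence is moderate, because the timing is inferred.

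**What to change.** Keep consent before delivery and change the assignment step as follows:

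- The next concealed block allocation is opened only after a spontaneous vaginal delivery is confirmed and the immediate postpartum pain score is recorded, promptly, and before the binder is issued.
- Every consented woman who is still eligible is randomised in sequence, and staff cannot see the allocation in advance.
- Consented women with a cesarean or operative vaginal delivery are counted and reported as screen failures outside the 140.

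This keeps the allowance of 10 for true dropouts. A minor gain is that the first postpartum pain score becomes a pre-allocation measure, although the SAP uses baseline pain only for a between-group comparison.

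**Cost.** Allocation must be available at any hour and without delay, because the protocol encourages binder wear for the first 24 hours postpartum and any delay shortens that period. More women must be consented than randomised, as in step 5 of the working. No extra assessments or randomised patients are needed.

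If assignment stays before delivery, state whether these women are replaced and how they are analysed, report the exclusions by arm, and restate power or the number to randomise. Keeping 130 analysable takes 130/(1 − loss): 145, 153, 163, 174 or 186 randomised at 10%, 15%, 20%, 25% or 30% assumed total loss. Later dropout needs an analysis-population rule under either timing.

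### No field or analysis is planned for allergic reaction, skin irritation or the reason a binder was removed; increased pain is seen only through routine pain scores

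*Protocol*

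**What the plan says.** **Harms anticipated.** The protocol's Risks section lists "Allergic reaction to fabric of abdominal binder", "Skin irritation" and "Increased discomfort or pain with use of abdominal binder". Under Mitigation of risks, women with a reaction are offered symptomatic treatment. Binder-arm women are encouraged to keep the binder on for 24 hours but may remove it at any time for irritation, worse pain or another adverse effect. That section does not ask for the event to be recorded.

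**Data collected.** Under Data collection plan, the hard-copy form holds participant identification and "basic demographic information, delivery information (see separate document), non-pharmacologic pain relief measures used". The second source is "Electronic medical record review for: pain scores, pain location, medications received", and the items listed beneath it end with "Compliance wearing the abdominal binder". No item is for an adverse event, a skin finding or an allergy.

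**Compliance record.** Under Study design & procedures, nurses document wearing of the binder, "making notes when the binder was removed and if/when it was put back on".

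**Pain record.** The same section has pain assessed "using a visual analog scale of 1-10 a minimum of every 4 hours", with location charted.

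**Analysis.** The SAP lists four comparisons: baseline characteristics, average pain on postpartum days 0 and 1, non-narcotic medication and narcotic medication. It mentions no harms, compliance or removals.

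**The concern.** The protocol treats these harms as likely enough to name and to be a reason for taking the binder off, yet the plan does not carry them into data collection or analysis. Two things are at stake.

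First, if the binder reduces pain or medication use, no count of skin or allergic events can be set beside that benefit.

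Second, removal determines exposure. If the result is null and many binders came off early, the plan gives removal times but need not give reasons. A binder that does not work then looks the same as one that women could not tolerate.

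Both kinds of information exist only at the bedside. If they are not written down then, they cannot be reliably reconstructed.

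**Working it through.** **1. Each harm traced through the plan**

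| Item | Data collection list | SAP |
|---|---|---|
| Allergic reaction | No field | No analysis |
| Skin irritation | No field | No analysis |
| Increased pain | Indirect: pain score and location, both arms | Indirect: average pain by day and arm |
| Discomfort other than pain | No field | No analysis |
| Time of binder removal | Yes, in compliance notes | No analysis |
| Reason for removal | Not required | No analysis |

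Two of the three named risks therefore have neither a field nor an analysis. The third is covered in part.

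**2. What the pain data can and cannot show**

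Suppose a fraction q of binder-arm women have their pain raised by δ points for a fraction t of the day, before they take the binder off. The shift in that arm's daily average is about q × δ × t. Early removal makes t small, and the scores taken afterwards, without the binder, enter the same average. If the other women benefit, the shift is offset further. The SAP comparison therefore estimates the net effect. It would show an overall worsening, but not a minority who were made worse and stopped. The documents give no values for q, δ or t, so none is assumed.

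**3. Size of the binder arm**

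The protocol states 65 per group, plus 10 for dropouts, for a total of 140. Taking a medium effect as d = 0.5 and a two-sided 0.05 level (both assumed, since the protocol gives neither):

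- Normal approximation: n = 2 × (1.96 + 0.84)² / 0.5² ≈ 63 per group.
- Exact t-test: 63.77, rounded up to 64 per group.
- Total: 2 × 65 + 10 = 140, so 70 per arm with equal allocation.

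The plan's figure is reproduced to within two women per group. The binder arm is thus 65 (if all dropouts are lost) to 70.

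**4. What recording the events would offer**

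For zero events in n women, the upper limit of the exact two-sided 95% interval is 1 − 0.025^(1/n):

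- n = 70: 1 − 0.025^(1/70) = 5.1%
- n = 65: 1 − 0.025^(1/65) = 5.5%

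A one-sided 95% limit, 1 − 0.05^(1/n), gives 4.2% and 4.5%. The two conventions should not be mixed in one report.

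The chance of seeing at least one event is 1 − (1 − p)^n. The documents give no event rate, so p is an assumed range:

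| True rate p | n = 65 | n = 70 |
|---|---|---|
| 1% | 48% | 51% |
| 2% | 73% | 76% |
| 5% | 96% | 97% |
| 10% | >99% | >99% |

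With systematic recording, a trial of this size would very probably detect reactions affecting 5% or more of women, and could easily miss those at 1%.

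**The case against.** A reader might infer that the trial collects no harms data and cannot report on safety at all. The documents do not support that, for these reasons:

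- **Pain is collected and compared.** Scores and locations are charted in both arms and average pain is an SAP outcome. A binder that worsened pain overall would show it in the trial's own main comparison. This stands. Individual attribution, and discomfort that is not pain, remain uncovered.
- **The nursing notes may contain reasons.** The protocol does not require a reason, but free notes do not exclude one. This stands, so the accurate statement is that the reason is not required. Optional notes would not give complete counts.
- **Medication records may show a trace.** All medications received are charted, so a reaction treated with a drug might be found. This stands in part. Nothing directs anyone to look, and untreated irritation leaves no trace.
- **The forms cannot be inspected.** The delivery information sits in a separate document that was not available. This limits certainty, although the protocol's description of the form names no adverse event content.
- **No aim depends on it.** The three aims concern pain and medication quantity, and the device is an external garment that can be removed at any time. This stands and sets the severity.

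Nor do the documents say that the binder is intended for routine use. They present it only as a possible non-drug option, so the point should not rest on that.

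**Conclusion.** The point holds in limited form. As described, the plan has no field and no analysis for allergic reaction or skin irritation, does not require a reason for removal, and has no harms or compliance summary. Increased pain is captured only as a net difference in daily averages between arms.

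The severity is minor: no test, estimate or sample size for the stated aims changes. What would be lost is a descriptive safety statement, with an upper limit of roughly 5.1% to 5.5% if no events occurred, and the ability to read a null result as lack of effect or as poor tolerance.

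This rests on the protocol's description of its forms being complete. The limits also assume equal allocation, a binder arm of 65 to 70, and that every woman is asked.

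**What to change.** Add two fields to the existing data collection sheet:

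- **(a)** Skin irritation or allergic reaction: yes or no, with time, in both arms. The standard-care arm supplies the background rate.
- **(b)** Reason for each binder removal: irritation, increased pain or discomfort, or other.

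The protocol should say who completes these fields, since it does not say who fills in the sheet and it lists compliance under record review.

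In the SAP, add one descriptive table with skin and allergic events by arm and removal reasons in the binder arm. Give counts and proportions with exact two-sided 95% confidence intervals. No hypothesis test is needed.

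The cost is slight extra charting and one table. Field (b) still misses women who keep the binder on despite discomfort; for them the routine pain scores remain the only record.
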